7.3. Long-Term Follow-up: 6, 12, 24, and 36 months (Post-Market Follow-up)

Follow-up data collection will be conducted at approximately 6, 12, 24, and 36 months post-transplant.

- **6, 12, 24, and 36 month Follow Up:** At approximately 6, 12, 24, and 36 months post-transplant, the patient will be evaluated at an office visit if this is the institution's standard of care, and, if not, by phone contact by the site. The patient's medical record will be reviewed to confirm patient's answers. This follow-up will collect the following information on transplanted recipients in the trial:
 - Patient and graft survival
 - Whether the patient was hospitalized after initial discharge, and, if so, the primary reason for the hospitalization and the length of stay; these data will be collected only for the 6-month follow-up timepoint.
 - Clinical diagnosis of BOS and method of diagnosis
 - Results of any standard of care or per-cause pulmonary function tests, bronchoscopies, or biopsies

The 6, 12, 24, and 36 months follow-up will be collected within +30 days of the designated period and will be recorded.

8. EVALUATION OF ADVERSE EVENTS

8.1. Evaluation of Lung Graft-Related Adverse Events

Lung Graft-Related Adverse Events are those which have any untoward effect on the health or safety of the patient and that are directly related to the transplanted lung graft. Lung graft-related adverse events will be collected from the time a subject is transplanted with a lung preserved on OCS™ Lung System until the completion of the 30-day follow-up or until initial hospital admission (if longer than 30 days), which is the window for assessment of safety endpoint. A lung graft-related adverse event will be followed until resolution or stabilization of the event.

8.2. Serious Adverse Events (SAEs)

An adverse event will be classified as serious if it meets any of the following criteria:

- Results in, leads to, or contributes to, a death
- Is life-threatening
- Results in permanent disability or incapacity (i.e., permanent impairment of a body function or permanent damage to a body structure)
- Requires patient re-hospitalization or prolongs initial hospitalization
- Necessitates medical or surgical intervention to preclude a permanent disability or incapacity
- Results in fetal distress, fetal death or a congenital anomaly/birth defect.

All SAEs will be followed until their resolution.

8.3. Anticipated and Unanticipated Adverse Events

The investigator will assess each adverse event for whether it is anticipated or unanticipated to the lung transplant procedure.

The following adverse events are associated with pulmonary transplant procedures and have been documented within the first 30 days after lung transplant, or until initial hospital admission (if longer than 30 days) and are, therefore, anticipated:

- Acute rejection
- Arrhythmia
- Bleeding (major)
- Hemodynamic instability
- Death
- Fever
- Primary Graft Dysfunction (PGD) (see Appendix 1)
- Respiratory failure
- Graft failure
- Focal or systemic major infection (bacterial, viral, fungal)
- Sepsis
- Emphysema
- Tracheobronchitis/pneumonitis/pneumonia
- Renal dysfunction
- Hyperammonaemia
- Malignancy (post-transplant lymphoproliferative disorder (PTLD)
- Multiple organ failure
- Myocardial infarction
- Neurological dysfunction
- Hepatic dysfunction
- Gall stones
- Pancreatitis
- Peptic ulceration

- Gastritis
- Gastro esophageal reflux disease (GERD)
- Aspiration
- Pneumothorax
- Hemothorax
- Pleural bleeding
- Pleural effusion
- Airway anastomotic complications (focal infection, necrosis/dehiscence, stenosis)
- Venous thromboembolism (deep venous thrombosis [DVT])
- Pulmonary embolism (PE)
- Pulmonary infarction
- Wound dehiscence
- Organ deemed not transplantable after retrieval
- Stroke
- Psychosis

8.4. Unanticipated Adverse Device Effect (UADE)

An UADE means any serious adverse effect on health or safety or any life-threatening problem or death caused by, or associated with, a device, if that effect, problem, or death was not previously identified in nature, severity, or degree of incidence in the investigational plan or application (including a supplementary plan or application), or any other unanticipated serious problem associated with a device that relates to the rights, safety, or welfare of subjects (21 CFR 812.3(s)).

8.5. Recording and Reporting of Adverse Event

All lung graft-related adverse events and serious adverse events are to be recorded on the case report forms. The description of the adverse event will include the date of onset, duration, severity, seriousness, the relationship of the event to the trial treatment, anticipated or not, and any treatment required. All SAEs will be followed until their resolution.

For all SAEs, the investigator is required to supply any additional data that may be deemed necessary by the Sponsor. Additionally, SAE and unanticipated adverse device effects (UADEs) should be reported to TransMedics, Inc., preferably within 48 hours of the time the investigator learns of the event, but in no case later than 5 working days. For any particular patient, the independent Medical Monitor if required to protect patient safety may specify a different follow-up period. The Sponsor is responsible for the classification and reporting of lung graft-related adverse events to the appropriate regulatory authorities, and for the on-going safety evaluation of the trial in accordance with ISO 14155 and governing regulatory requirements.

8.6. Relationship of an Adverse Events to OCSTM Lung System

The investigator or designee will assess the relationship of the AE to the OCSTM Lung System or to the standard of care, methods of preservation. The relationship will be assessed using the following categories:

- **Definitely Related:** There is a reasonable causal and temporal relationship between preservation with the OCSTM Lung System or with preservation with the standard of care and the adverse event.

- **Probably Related:** It is more likely than not that there is a reasonable causal relationship between preservation with the OCS™ Lung System or with preservation with the standard of care and the adverse event.
- **Possibly Related:** There is a reasonable relationship with preservation with the OCST™ Lung System or with preservation with the standard of care and the adverse event, but the causal relationship is unclear or lacking.
- **Not Likely Related:** There is a temporal relationship with preservation with the OCST™ Lung System or with preservation with the standard of care and the adverse event, but there is not a reasonable causal relationship between the trial device and the event.
- **Unrelated:** There is no relationship between preservation with the OCST™ Lung System or with preservation with the standard of care and the adverse event.

8.7. Severity

The investigator will rate the severity of the adverse event using the following categories:

- **Mild:** The adverse event is transient and/or easily tolerated by the subject.
- **Moderate:** The adverse event causes the subject discomfort and interrupts the subject's usual activities.
- **Severe:** The adverse event causes considerable interference with the subject's usual activities.

8.8. Pre-Existing Conditions

Pre-existing diseases or conditions will not be reported as adverse events unless there has been a substantial increase in severity or frequency of the problem that cannot be attributed to the expected progression of the disease or condition.

8.9. Clinical and Laboratory Changes

The investigator will review the results of all clinical and laboratory tests as they become available. For each laboratory test result, the investigator will ascertain if this is an abnormal (i.e., clinically significant) change from baseline for that individual subject. This determination, however, does not necessarily need to be made the first time an abnormal value is observed. The investigator may repeat the laboratory test or request additional tests to verify the results of the original laboratory tests. If this laboratory value is determined to be clinically significant change from baseline for that subject, this will be considered an adverse event.

9. STATISTICAL METHODS

9.1. General

Continuous variables will be summarized using descriptive statistics, specifically the mean, median, standard deviation, minimum, and maximum. Categorical variables will be summarized using frequencies and percentages.

Missing outcomes, although not expected, will be addressed through multiple imputation so that analyses are based on complete data.

9.2. Analysis Populations

9.2.1. Transplanted Recipient Population

The transplanted recipient population will consist of all subjects who are transplanted in the trial. Additional supportive analyses of all effectiveness and safety endpoints will be based on the transplanted recipient population.

9.2.2. Per-Protocol (PP) Population

The Per-Protocol (PP) population will consist of all subjects who are transplanted without a major protocol violation. Major protocol violations would be considered:

- Ineligible for the study according to the recipient inclusion and exclusion criteria
- Ineligible for the study according to the donor organ inclusion and exclusion criteria
- Failure to complete adequate post-transplant assessments to support the primary effectiveness and primary safety endpoints
- Failure to follow the IFU for the OCSTM Lung System
- Failure to meet Donor Lung Acceptance for Transplantation after assessment on the OCSTM Lung System, as outlined in Section 6.5.

The primary analysis of all endpoints will be based on the PP population, which is appropriate given that the comparator rate is derived from the Control arm of the PP population from the INSPIRE trial. Supportive analyses will be conducted using the Transplanted Recipient population.

9.3. Analysis of Effectiveness Endpoints

There are two co-primary hypotheses for this trial.

9.3.1. Co-Primary Effectiveness Endpoint #1

The first co-primary hypothesis is that the proportion of transplanted recipients of lungs preserved using the OCSTM Lung System surviving at Day 30 and at initial hospital discharge post-transplantation (whichever occurs later) is greater than a performance goal based on the corresponding proportion of patients in the Per-Protocol population of the Control arm of the INSPIRE trial (0.939) with a margin of 0.12 (12%).

The determination of the margin (12%) is based on the following:

- The estimate observed in the Control arm of the INSPIRE trial [93.9% (169/180)] serves as the target for the first co-primary endpoint.
- The 99% exact binomial confidence interval around the INSPIRE outcome (87.8% to 97.6%) provides an indication of conservative variability for eligible organs under standard of care with a lower bound about 6% away from the target.

- The lack of historical data and limited knowledge with respect to non-ideal donor lung transplantation suggests a 12% margin (i.e., doubling the lower bound distance of 6% associated with the INSPIRE estimate).

The formal statistical hypothesis test is as follows:

$$H_0: \pi_{OCS\ Lung} \leq 0.819$$

$$H_1: \pi_{OCS\ Lung} > 0.819$$

where $\pi_{OCS\ Lung}$ is the proportion of transplanted recipients alive Day 30 and at initial hospital discharge.

This co-primary effectiveness endpoint will be summarized using a count and percentage with an exact 95% confidence interval for the percentage based on the binomial distribution. A one-sided exact binomial test at the 0.025 significance level will be performed to test the null hypothesis H_0 .

9.3.2. Co-primary Effectiveness Endpoint #2

The second co-primary hypothesis is that the Utilization Rate (defined in Section 4.1 above) is greater than a performance goal of 0.54 (54%), which is based on the utilization rate reported for XVIVO in the NOVEL Trial.² The formal statistical hypothesis test is as follows:

$$H_0: \pi_{OCS\ Lung} \leq 0.54$$

$$H_1: \pi_{OCS\ Lung} > 0.54$$

where $\pi_{OCS\ Lung}$ is the observed utilization rate in the EXPAND trial.

The appropriateness of the performance goal of 54% is based on the following:

- The 54% rate is the only published data available on utilization rate for non-ideal donor lungs.⁵⁶
- The donor lung inclusion/exclusion criteria are similar to those used for the XVIVO NOVEL study. Where differences exist, they tend to make the donor lungs more challenging for EXPAND II vs NOVEL. For example:
 - EXPAND II will enroll DCD donors with any $\text{PaO}_2/\text{FiO}_2$ ratio, while the NOVEL study only included DCD donors with $\text{PaO}_2/\text{FiO}_2$ ratio ≥ 300 mmHg.
 - EXPAND II will include older donors (age > 55 years) while NOVEL did not have an inclusion criterion based on donor age. Donor age > 55 years old is known to have a negative impact on outcomes after lung transplantation.⁴
- Finally, this co-primary endpoint is designed to show superiority of the OCSTM Lung System to the XVIVO EVLP device. Demonstrating superiority to the only published data on utilization in the non-ideal donor lung population is a rigorous and appropriate test of a new technology.

This co-primary effectiveness endpoint will be summarized using a count and percentage with an exact 95% confidence interval for the true percentage based on the binomial distribution. A one-sided exact binomial test at the 0.025 significance level will be performed to test the null hypothesis, H_0 .

9.4. Secondary Effectiveness Endpoints

The secondary effectiveness endpoints will be summarized using counts and percentages and an exact 95% confidence interval for the true percentage based on the binomial distribution..

9.5. Other Effectiveness Endpoints

These endpoints will be summarized using relevant descriptive statistics (e.g., mean, standard deviation, count, percentage, 95% CI).

9.6. Analysis of Safety

9.6.1. Primary Safety Endpoint

Safety will be analyzed principally by examination of the frequency of adverse events. In particular, the primary safety endpoint is the number of lung graft-related serious adverse events (SAEs) up to the 30-day follow-up or until initial hospital admission (if longer than 30 days) after transplantation per subject will be analyzed. This endpoint is defined to consist of the following adverse events (at most one per type), if they are serious adverse events (see Appendix 3):

- Biopsy proven moderate or severe acute rejection
- Respiratory failure requiring prolonged intubation or reintubation
- Bronchial anastomotic complications
- Major pulmonary-related infection

The primary safety hypothesis is that the mean number of lung graft-related SAEs up to the 30-day follow-up after transplantation is less than a performance goal based on the corresponding mean in the Per-Protocol population of the Control arm of the INSPIRE trial (0.29 events per subject) with a margin of 0.7 events. Specifically:

$$H_0: \mu_{OCS\ Lung} \geq 0.99$$

$$H_1: \mu_{OCS\ Lung} < 0.99$$

where $\mu_{OCS\ Lung}$ is the mean number of lung graft-related SAEs through 30 days post-transplantation among transplanted recipients.

This endpoint will be summarized using descriptive statistics, specifically the mean, median, standard deviation, minimum, maximum, and a 95% confidence interval for the mean based on the t-distribution. A one-sided one-sample t-test at the 0.025 significance level will be performed to test the null hypothesis H_0 .

9.6.2. Other Adverse Events

In addition, the numbers and percentages of subjects experiencing at least one lung graft-related AE, at least one severe AE, at least one device-related AE, at least one unanticipated AE, and at least one serious AE, and the number and percentage of deaths will all be tabulated.

The number of adverse events and the number and percentage of subjects experiencing adverse events will be tabulated by system organ class and preferred term using MedDRA. A similar analysis will be performed for serious AEs. The number and percentage of subjects experiencing AEs will also be tabulated by system organ class and preferred term and the relationship of the

adverse event to the device (focusing on differentiating adverse events deemed definitely and probably related to the device). Similar analyses will be performed by the severity of the adverse event.

9.7. Sample Size Determination

The sample size for this trial was determined based on providing adequate statistical power for hypothesis testing of the two co-primary effectiveness endpoints. All sample size calculations were performed using PROC POWER in SAS.

For the first co-primary endpoint, the calculations assumed a one-sided exact binomial test, an alpha level of 0.025, a control-based rate of 0.939 with a margin of 0.12 (to derive the performance goal of 0.819), a true survival rate for OCST™ of 0.939, and desired power of 90%. Based on these specifications, the required sample size was determined to be 84 transplanted recipients.

For the second co-primary endpoint, the calculations assumed a one-sided exact binomial test, an alpha level of 0.025, a performance goal of 0.54, a utilization rate of 72% for OCST™, and desired 90% power. Based on these specifications, the required sample size was determined to be 84 transplanted recipients

In order to ensure that a sufficient number of subjects are evaluable in the per-protocol population of the trial, 90 transplanted recipients in the study is expected to provide adequate power to evaluate the two co-primary effectiveness objectives given the assumptions described.

Due to multiple primary endpoints, the Hochberg Method⁵⁵ will be used to control familywise error. The p-values for each of the co-primary endpoints will be ordered from highest to lowest. If the highest p-value is less than 0.025 then both endpoints achieve statistical significance and the null hypothesis of each co-primary endpoint can be rejected. If not, then the lower of the two p-values will be assessed against a significance level of 0.0125. If the adjusted significance level of 0.0125 is applied to any of the co-primary endpoints, the power of that analysis will be greater than 85%. Therefore, the study will be considered successful in either of the two scenarios described above.

With regard to the primary safety endpoint, the pre-specified safety margin of 0.7 events per patient, the estimated mean of 0.29 events per patient (with an estimated standard deviation of 2.0), a one-sided alpha of 0.025, and the sample size of 90 transplanted recipients results in power greater than 90% when considering a one-sample t-test on the mean.

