Other Endpoints	
 • Total ischemia and cross-clamp times • Duration of initial post-transplant invasive mechanical ventilation • Length of initial post-transplant ICU stay • Length of initial post-transplant hospital stay • PGD Scores at T0, T24, T48, and T72 hours post-transplantation • Incidence of BOS at 6, 12, 24, and 36 months post-transplantation (including post-market follow-up) • All-cause mortality at 6, 12, 24, and 36 months post-transplantation (including post-market follow-up) • Lung graft-related mortality at 6, 12, 24, and 36 months post-transplantation (including post-market follow-up)
Primary Safety Endpoint	
The primary safety endpoint is the number of lung graft-related serious adverse events through the 30-day follow-up or until initial hospital admission (if longer than 30 days) after transplantation per subject, consisting of the following serious adverse events (at most one per type) as described in Appendix 3:
 
 • Biopsy proven moderate or severe acute rejection • Respiratory failure requiring prolonged intubation or reintubation • Bronchial anastomotic complications • Major pulmonary-related infection
Follow-up	All patients will be followed for up to 3 years post-transplant (including post-market follow-up).

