----------------------------	--

	
 • Respiratory failure • Bronchial anastomotic complication • Major pulmonary-related infection 
The primary safety hypothesis is that the mean number of lung graft-related SAEs up to the 30-day follow-up or until initial hospital admission (if longer than 30 days) after transplantation is less than a performance goal based on the corresponding mean in the Per-Protocol population of the Control arm of the INSPIRE trial (0.29 events per subject) with a margin of 0.7 events. Specifically:
 $H_0: \mu_{OCS\ Lung} \geq 0.99$ $H_1: \mu_{OCS\ Lung} < 0.99$ 
where $\mu_{OCS\ Lung}$ is the mean number of lung graft-related SAEs through 30 days post-transplantation among transplanted recipients.
 
This endpoint will be summarized using descriptive statistics, specifically the mean, median, standard deviation, minimum, maximum, and a 95% confidence interval for the mean based on the t-distribution. A one-sided one-sample t-test at the 0.025 significance level will be performed to test the null hypothesis H_0. In addition to the primary safety endpoint, all adverse events will be summarized using standard descriptive statistics.

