The safety endpoint is the number of LGRSAEs through the 30-day follow-up period after transplantation per subject. Thirteen (13) subjects experienced 14 LGRSAEs within 30 days post-transplant. Eleven (11) were respiratory failure, which includes protracted ventilation and 3 were major pulmonary infections. There were no incidences of bronchial anastomotic complication or acute rejection (biopsy-proven). These rates of LGRSAEs are not unexpected, given the fact that this study focuses on non-ideal donor lungs. Long-term follow-up is continuing.

[figure not shown]
Table 3: Safety Endpoint Results

Lung Graft-Related SAEs (LGRSAEs)	Incidence Rate
Subjects with at least one LGRSAE within 30 days	13/56 (23%)
Respiratory failure/Protracted ventilation	11/56 (20%)
Major pulmonary-related infection	3/56 (5%)
Bronchial anastomotic complication	0/56 (0%)
Biopsy-proven acute rejection	0/56 (0%)

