### **3.4. Determination of Sample Size**

The sample size for this trial was determined based on providing adequate statistical power for hypothesis testing of the two co-primary effectiveness endpoints. All sample size calculations were performed using PROC POWER in SAS.

For the first co-primary endpoint, the calculations assumed a one-sided exact binomial test, an alpha level of 0.025, a control-based rate of 0.939 with a margin of 0.12 (to derive the performance goal of 0.819), a true survival rate for OCS™ of 0.939, and desired power of 90%. Based on these specifications, the required sample size was determined to be 84 transplanted recipients.

For the second co-primary endpoint, the calculations assumed a one-sided exact binomial test, an alpha level of 0.025, a performance goal of 0.54, a utilization rate of 72% for OCS™, and desired 90% power. Based on these specifications, the required sample size was determined to be 84 transplanted recipients

In order to ensure that a sufficient number of subjects are evaluable in the per-protocol population of the trial, 90 transplanted recipients in the study are expected to provide adequate power to evaluate the two co-primary effectiveness objectives given the assumptions described.

Due to multiple primary endpoints, the Hochberg Method will be used to control familywise error. The p-values for each of the co-primary endpoints will be ordered from highest to lowest. If the highest p-value is less than 0.025 then both endpoints achieve statistical significance and the null hypothesis of each co-primary endpoint can be rejected. If not, then the lower of the two p-values will be assessed against a significance level of 0.0125. If the adjusted significance level of 0.0125 is applied to any of the co-primary endpoints, the power of that analysis will be greater than 85%. Therefore, the study will be considered successful in either of the two scenarios described above.

With regard to the primary safety endpoint, the pre-specified safety margin of 0.7 events per patient, the estimated mean of 0.29 events per patient (with an estimated standard deviation of 2.0), a one-sided alpha of 0.025, and the sample size of 90 transplanted recipients results in power greater than 90% when considering a one-sample t-test on the mean.

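### The primary safety power statement rests on an SD of 2.0 that a 0-4 count with mean 0.29 cannot have (maximum 1.04), so the 0.99 goal looks stricter than it is; separately, the safety window is defined in two ways

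*Protocol*

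**What the plan says.** **Endpoint and goal.** Protocol 9.6.1 lists four types of lung graft-related serious adverse event and counts each at most once per subject: "This endpoint is defined to consist of the following adverse events (at most one per type), if they are serious adverse events". The goal is built from the INSPIRE control arm, "0.29 events per subject) with a margin of 0.7 events", so the null value is 0.29 + 0.7 = 0.99. The test is a one-sample t-test at one-sided 0.025.

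**Power.** Protocol 9.7, SAP 3.4 and the synopsis give the same inputs, namely "the estimated mean of 0.29 events per patient (with an estimated standard deviation of 2.0", and conclude that "the sample size of 90 transplanted recipients results in power greater than 90% when considering a one-sample t-test on the mean". No source is given for the SD.

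**Earlier data on the same event types.** Protocol 1.4.4 reports on 56 EXPAND I recipients: "Thirteen (13) subjects experienced 14 LGRSAEs within 30 days post-transplant".

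**Window.** The synopsis counts events "through the 30-day follow-up or until initial hospital admission (if longer than 30 days) after transplantation per subject, consisting of" the four types. Protocol 4.4 and 8.1, SAP 4.4, and the endpoint sentences of Protocol 9.6.1 and SAP 13.1 also run past Day 30. Appendix 3, the hypothesis sentences in Protocol 9.6.1 and SAP 13.1, and the definition of the tested mean in all three places where it appears stop at 30 days.

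**The concern.** An SD of 2.0 is far too large for a count that is nearly always 0 or 1 and cannot exceed 4. An overstated SD does no harm to a sample size that was set elsewhere, but it distorts the picture of the test. It suggests roughly a 9% chance of missing the goal at the control mean. Carried to other true means, it suggests that a substantial worsening would often fail. If the real SD is much smaller, the 0.99 goal, which is 0.99/0.29 = 3.4 times the control mean, is easy to meet. A met goal could then be taken as stronger safety evidence than it is, in a single-arm trial of non-ideal lungs.

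The window matters for a different reason. If events after Day 30 in a long first admission count in one section and not in another, two analysts could compute different values of the primary safety endpoint. Neither could be sure that theirs matches the benchmark of 0.29.

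**Working it through.** **1. The plan's own figure.** Inputs from Protocol 9.7: mean 0.29, goal 0.99, SD 2.0, n = 90, one-sided 0.025. The noncentrality is 0.7 × √90 / 2.0 = 3.32 with 89 df, and power is 90.7%. The statement of more than 90% reproduces. At n = 84, the number required for the effectiveness endpoints, the same SD gives 88.7%. I show both sizes because Protocol 9.2.2 makes the per-protocol population primary for all endpoints, while SAP 13.1 runs safety on all transplanted recipients.

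**2. Largest possible SD.** For a variable confined to 0-4 with mean m, the SD is at most √(m(4 − m)).
- m = 0.29: √(0.29 × 3.71) = √1.076 = 1.04.
- Over all means the ceiling is √(2 × 2) = 2.0. It is reached only at mean 2, with half the subjects at 0 and half at 4.

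**3. What EXPAND I implies.** With each type counted once, 14 events in 13 of 56 subjects means 43 with none, 12 with one and 1 with two. The mean is 14/56 = 0.25. The variance is (16 − 14²/56)/55 = 12.5/55 = 0.227, so the SD is 0.48.

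**4. Probability of meeting the goal.** The SD 2.0 row uses the noncentral t. The other rows apply the planned t-test to actual 0-4 counts. The doubled mean, 2 × 0.29 = 0.58, is my scenario and is not in the documents.

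| Distribution | Mean 0.29, n = 90 | Mean 0.29, n = 84 | Mean 0.58, n = 90 | Mean 0.58, n = 84 |
|---|---|---|---|---|
| SD 2.0 as stated | 90.7% | 88.7% | 48.6% | 45.9% |
| Independent types (four equal, or EXPAND I 11:3 mix) | about 100% | about 100% | 99.9-100% | 99.8-100% |
| Correlated types, rho 0.1 | about 100% | about 100% | 99.2% | 98.8% |
| Correlated types, rho 0.2 | about 100% | about 100% | 97.6% | 96.8% |
| Correlated types, rho 0.3 | about 100% | about 100% | 95.3% | 93.9% |
| All-or-none (every subject 0 or 4) | 99.93% | 99.72% | 77.3% | 67.0% |

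The correlated rows use a beta-binomial count. The all-or-none row is exact. At n = 90 the test passes with at most 15 affected subjects, so at mean 0.58 the pass rate is P(Bin(90, 0.58/4) ≤ 15) = 77.3%. At n = 84 the limit is 13 subjects.

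**5. Why the SD matters so much.** The largest observed mean that passes at n = 90 is 0.99 − 1.987 × SD/√90. With SD 2.0 this is 0.57, just under the doubled mean. With SD 0.70, the value for four equal independent types at mean 0.58, it is 0.84.

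**6. The windows side by side.**

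| Runs past Day 30 | Stops at 30 days |
|---|---|
| Synopsis, endpoint and hypothesis sentence | Synopsis, definition of the tested mean |
| Protocol 4.4 and 8.1 | Protocol Appendix 3 |
| Protocol 9.6.1, endpoint sentence | Protocol 9.6.1, hypothesis sentence and definition of the mean |
| SAP 4.4 | |
| SAP 13.1, endpoint sentence | SAP 13.1, hypothesis sentence and definition of the mean |

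The benchmark does not settle it. The synopsis ties 0.29 to the longer window: "The primary safety hypothesis is that the mean number of lung graft-related SAEs up to the 30-day follow-up or until initial hospital admission". Protocol 9.6.1 and SAP 13.1 tie the same 0.29 to 30 days. Protocol 1.4.3 describes INSPIRE's own safety endpoint as 30-day but does not give 0.29.

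**The case against.** The strongest reply is that nothing in the trial depends on the SD. The sample size was set on the two effectiveness endpoints, and too large an SD is a conservative input. The test will use the observed SD, and the goal and margin are printed. The planned 95% confidence interval would show directly whether a doubling is excluded: at mean 0.29, SD 0.50 and n = 90 its upper limit is 0.29 + 1.987 × 0.50/√90 = 0.395, below 0.58. All of this stands, and it limits the point to a wrong input and a misleading impression.

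Three stronger readings are tempting and are not supported.
- A reader might infer that the power claim is false or the trial underpowered for safety. At n = 90 the claim is true, and true power is higher than stated.
- A reader might infer that a doubled mean would pass practically always. The 99.9-100% figure needs independent event types. Respiratory failure and pulmonary infection arise in the same graft, and a single double event among 56 EXPAND I subjects cannot rule out modest correlation.
- A reader might infer that the plan claims to exclude a doubling. It states power at 0.29 only, and its hypothesis is only that the mean lies below 0.99.

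The plan derives its 12% survival margin but gives no derivation for the 0.7. That is missing detail rather than an error, and I make no point of it.

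On the window, Protocol 8.1 expressly names the longer period as the one for the safety endpoint. Protocol 4.1 and SAP 4.1 use initial hospital admission for the whole stay through discharge, so reading the phrase as ending the window at the start of the stay is strained. That helps with the phrase, but it does not remove the conflict with Appendix 3 and the definition of the tested mean.

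**Conclusion.** Two errors stand and should be corrected; neither is a threat to the trial.

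The SD of 2.0 is impossible for this endpoint at the stated mean. That rests only on the 0-4 range and the mean of 0.29, with no assumption about how events cluster. Power at the control mean is close to 100%, not just above 90%. In the all-or-none extreme it is about 99.9% at n = 90 and 99.7% at n = 84. A numerical search over 213 feasible distributions found nothing below 99.90% and 99.72% respectively, but that is a search and not a proof.

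The size of the distortion at a doubled mean depends on correlation between event types, which the documents do not give. At n = 90 the stated SD yields 49%, against about 95-100% for correlations from 0.3 down to zero and 77% in the all-or-none case. In every case in the table the goal is easier to meet than the stated SD suggests, so a met goal should not be read as excluding a doubling.

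The window contradiction is plain on the text. The documents do not establish which window is right, nor which one the INSPIRE mean of 0.29 covers.

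**What to change.** **Power statement (synopsis, Protocol 9.7, SAP 3.4).**
- Replace SD 2.0 with a feasible value, about 0.5, and note the ceiling of 1.04.
- Restate power at mean 0.29 as above 99% for n = 84 to 90.
- Beside it, give the probability of meeting the goal at twice the control mean, with the correlation assumption used.

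This is a wording change. Sample size, test, alpha and goal stay as they are.

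**Safety window (synopsis, Protocol 4.4, 8.1, 9.6.1 and Appendix 3, SAP 4.4 and 13.1).**
- The sponsor should check the INSPIRE source and state which window the mean of 0.29 covers.
- All of these sections should then be reconciled to one window matching that benchmark, before data are analysed.
- The phrase about initial hospital admission should say plainly whether it means the whole stay through discharge.

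The cost is one source check. Depending on the answer, it is a wording correction or an amendment to the definition of the primary safety endpoint.
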